### 10.3 Insurance

Insurance may be contracted according to local regulatory requirements.

**PAGE 74 OF 287** 

# 11 MANAGEMENT AND REPORTING OF ADVERSE EVENTS, SERIOUS ADVERSE EVENTS, SPECIAL SITUATIONS AND ADVERSE EVENTS OF SPECIAL INTEREST FOR EXPOSED PARTICIPANTS

### 11.1 Definitions

### 11.1.1 Adverse Event

### **AE Definition**

An AE is any untoward medical occurrence in a patient/participant, administered a medicinal product (palovarotene) and which does not necessarily have a causal relationship with this treatment.

NOTE: An AE can therefore be any unfavourable and unintended sign (e.g. an abnormal laboratory finding), symptom, or disease temporally associated with the use of the medicinal product, whether or not related to the medicinal product.

### Events Meeting the AE Definition

Any abnormal laboratory test results (haematology, clinical chemistry, or urinalysis) or other safety assessments (e.g. electrocardiograms, radiological scans, vital signs measurements), including those that worsen from Baseline, considered clinically significant in the medical and scientific judgment of the investigator (i.e. not related to progression of underlying disease).

Exacerbation of a chronic or intermittent pre-existing condition including either an increase in frequency and/or intensity of the condition.

New condition detected or diagnosed after study treatment administration even though it may have been present before the start of the study.

Signs, symptoms, or the clinical sequelae of a suspected drug-drug interaction.

Signs, symptoms, or the clinical sequelae of a suspected overdose of either study treatment or a concomitant medication. Overdose per se will not be reported as an AE/SAE unless it is an intentional overdose taken with possible suicidal/self-harming intent. Such overdoses should be reported regardless of sequelae.

For studies involving marketed products in established indications:

The signs, symptoms and/or clinical sequelae resulting from lack of effectiveness will be reported as AE or SAE if they fulfil the definition of an AE or SAE.

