# 9.2.6 Registry Study Schedule

The schedule of assessments that will be collected during the FOPal registry study for exposed naïve, exposed non-naïve, and unexposed participants is summarised in Table 2, Table 3 and Table 4 respectively. As this is a non-interventional, observational, prospective and retrospective registry study designed to collect and assess real-world data, these assessments are not mandated by this protocol. If some assessments are not routinely performed by the investigator, the data will not be captured in the eCRF.

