**PAGE 39 OF 287** 

 Table 2
 Schedule of Assessments: Exposed Naïve Participants

Assessment/Procedure	Baseline Visit	Follow-Up Visits (as per routine clinical practice[a])/ End of Study Visit
Clinic visit or telephone/video contact visit	X	X
Informed consent [b]	X	
Inclusion/exclusion criteria	X	
Baseline demographics	X	
Physical examination [c,d]	X	X
Medical or surgical history	X	
FOP history	X	
Growth status assessment (bone age, knee height and epiphyseal status) [d,e]	X	X
Tanner staging [d,e]	X	X
Linear height [f] and weight [d]	X	X
Vital signs [d,g]	X	X
Pregnancy testing [h]	X	X
Prior /concomitant medications [i]	X	X
Concomitant surgery and non-drug therapies	X	X
Prior use of palovarotene (investigational product)	X	
Palovarotene dose for chronic and flare-up treatment [j]	X	X
Spirometry and DLCO test [d,k]	X	X
CAJIS [d]	X	X
Movement mobility history (including flare-ups [1])	X	
Movement mobility changes (including flare-ups)	X	X
Spinal health assessment [m]	X	X
AEs, SAEs, Special Situations, and AESIs [n]	X	X
Participant Questionnaires:		
FOP-PFQ assessment [o]	X	X
PROMIS Global Health Scale [o]	X	X
FOP assistive devices assessment [o]	X	X

AE=Adverse Event; AESI=Adverse Event of Special Interest; CAJIS=Cumulative Analogue Joint Involvement Scale; CT= Computed Tomography; DLCO=Diffusion Capacity of the Lung for Carbon Monoxide; FEV1=Forced Expiratory Volume in one second; FOP=Fibrodysplasia Ossificans Progressiva; FOP-PFQ=FOP-Physical Function Questionnaire; FVC=Forced Vital Capacity; HEENT= head, eyes, ears, nose and throat; PI=Prescribing Information; PROMIS=Patient-Reported Outcomes Measurement Information System; SAE=Serious Adverse Event; SS=Special Situation.

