## 9.3 Endpoints and Variables

## 9.3.1 Endpoints

# 9.3.1.1 Primary Endpoints

- Incidence and description of all TEAEs, whether or not they are considered as related to palovarotene;
- Incidence and description of all serious TEAEs, whether or not they are considered as related to palovarotene;
- Incidence and description of all nonserious TEAEs whether or not they are considered as related to palovarotene;
- Incidence and description of all serious and nonserious treatment-related TEAEs.

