#### 9.7.3.2 Analysis of Primary Endpoints – Safety Evaluation

Adverse Events, Special Situations and Adverse Events of Special Interest

All AEs, Special Situations and AESIs will be included in the participant data listings using the Safety Exposed Population. Analyses and summary tables will be presented in the Safety Exposed Population.

Adverse events will be coded according to MedDRA and will be classified by PT and SOC. Adverse events listings will be presented by participant, SOC and PT.

The incidence of all reported TEAEs, serious and nonserious treatment-related TEAEs, all serious TEAEs, all nonserious TEAEs, AEs leading to death, AEs leading to treatment discontinuation, Special Situations and AESIs will be tabulated separately. In addition, summary tables for TEAEs will be presented by maximum intensity and drug relationship (investigator-reported causality assessment).

A TEAE is defined as any AE that occurs from the first dose of marketed palovarotene intake until the last palovarotene intake + 30 days if:

- It was not present prior to receiving the first dose of palovarotene; or
- It was present prior to receiving the first dose of palovarotene but the event worsened during treatment with palovarotene.

All TEAEs will be flagged in the AE listings.

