**PAGE 76 OF 287** 

Any radiological or clinical fracture, or PPC, must be reported as serious (seriousness criteria should be "important medical event" if no other seriousness criteria are present (e.g. hospitalisation)).

Is a suspected transmission of any infectious agent via an authorised medicinal product

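### Fracture and AESI incidence mixes vertebral fractures that pre-date the first dose with new ones, because the fracture tables are not split by prior spinal imaging

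*Protocol*

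**What the plan says.** Section 11.1.1 of the protocol, among the events that meet the adverse event (AE) definition, includes: "New condition detected or diagnosed after study treatment administration even though it may have been present before the start of the study". Section 11.1.2 adds: "Any radiological or clinical fracture, or PPC, must be reported as serious". Fractures are also an AESI (sections 9.3.2.5 and 11.1.4).

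Section 9.7.3.2 defines a TEAE as "any AE that occurs from the first dose of marketed palovarotene intake until the last palovarotene intake + 30 days", subject to one of two conditions. The first reads: "It was not present prior to receiving the first dose of palovarotene; or". The second, which covers events that already existed, reads: "It was present prior to receiving the first dose of palovarotene but the event worsened during treatment with palovarotene". TEAEs are flagged within the AE listings. The same section tabulates the incidence of AESIs, and section 9.7.3.4 the incidence of all reported fractures, with further tables by maximum intensity and drug relationship. Neither the AESI nor the fracture tabulation is limited to treatment-emergent events or split by whether an earlier image exists. One of the four primary endpoints in section 9.3.1.1 is: "Incidence and description of all serious TEAEs, whether or not they are considered as related to palovarotene".

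Spinal assessment is scheduled at Baseline and follow-up for exposed naïve participants (Table 2). For non-naïve participants it is collected at the first marketed intake and at follow-up (Table 3). Section 9.2.6 says of the scheduled assessments that "these assessments are not mandated by this protocol". Section 9.3.2.7 ties spinal imaging to clinical practice and the product label. Section 9.7.3.5 sends the imaging results to participant listings only.

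**The concern.** Section 7.3.1 names radiological vertebral fracture as a risk associated with palovarotene, found by retrospective reading of whole-body CT data. Detection therefore depends on imaging. Section 7.1 lists fractures among the morbidity of FOP itself (falls, immobility, prednisone use), so some participants may plausibly carry an old, unrecognised vertebral fracture when they start treatment.

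If such a fracture first appears on an on-treatment image, it is an AE, an AESI and serious, and it enters the fracture incidence table. Nothing in that table shows the reader whether it was new. The reported incidence of an identified risk would then depend partly on how often sites image before dosing, and the error runs upward. The information that would separate the two kinds of fracture is collected but is not linked to the fracture tables.

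**Working it through.** **1. Follow one event through the rules.** Take a vertebral fracture that was present before the first dose and is first seen on an on-treatment image.

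| Rule | Section | Result |
|---|---|---|
| AE | 11.1.1 | Yes, even though it was already there |
| Serious | 11.1.2 | Yes, as any radiological fracture |
| AESI | 9.3.2.5, 11.1.4 | Yes |
| Counted in AESI incidence | 9.7.3.2 | Yes; no treatment-emergent restriction stated |
| Counted in all reported fractures | 9.7.3.4 | Yes; no split by prior image |
| TEAE, pre-dose image shows it | 9.7.3.2 | No, unless it worsened |
| TEAE, no pre-dose image | 9.7.3.2 | Cannot be decided from the wording |

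The mixing in the AESI and fracture tables follows from the stated rules. An effect on serious TEAEs is only possible: it depends on how a fracture of unknown onset is classed.

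**2. Is a pre-dose image assured?** It is scheduled for both exposed groups but required for neither (section 9.2.6). The Baseline Visit may be by telephone or video (section 9.2.7), and section 9.9 accepts that key data may be missing.

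**3. Ceiling for all TEAEs.** Section 7.3.1 gives 97.8% of exposed participants aged ≥8/10 years with reactions in the skin system organ class. If that carries over, the room left is 1 − 0.978 = 0.022, and 67 × 0.022 = 1.5 participants.

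**4. Possible size for fractures.** The protocol states no fracture prevalence and no imaging coverage, so there is no figure to reproduce. As an illustration on assumed values only, let p be the share with an old fracture, m the share of those without a pre-dose image, and i the share of those imaged on treatment. With the minimum exposed cohort of 67 (section 9.7.2), old fractures that cannot be told from new ones number 67 × p × m × i.

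| p | m | i | Participants | Percentage points |
|---|---|---|---|---|
| any | 0% | any | 0 | 0 |
| 5% | 25% | 50% | 0.4 | 0.6 |
| 10% | 50% | 50% | 1.7 | 2.5 |
| 10% | 50% | 100% | 3.4 | 5.0 |
| 20% | 50% | 100% | 6.7 | 10.0 |
| 30% | 100% | 100% | 20.1 | 30.0 |

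**5. Possible size for serious TEAEs.** This applies only if fractures of unknown onset are counted as treatment-emergent. With an assumed true incidence s = 20%, i = 100% and independence, the observed incidence is 1 − (1 − s)(1 − p × m):
- p = 5%, m = 25%: 1 − 0.80 × 0.9875 = 21.0%
- p = 10%, m = 50%: 1 − 0.80 × 0.95 = 24.0%
- p = 20%, m = 50%: 1 − 0.80 × 0.90 = 28.0%
- p = 30%, m = 100%: 1 − 0.80 × 0.70 = 44.0%

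**6. Schedule check.** For non-naïve participants, Table 3 leaves the Baseline cell for spinal assessment blank. Section 9.2.7.1 lists that assessment at the first marketed intake and at the Baseline Visit. The two disagree.

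**The case against.** A reader might infer that section 11.1.1 contradicts the TEAE rule in section 9.7.3.2. It does not. TEAEs are a flagged subset of AEs, and an AE that is not a TEAE is the normal split.

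A reader might also infer that an old fracture without a pre-dose image will be counted as treatment-emergent because its onset defaults to the detection date. No section states such a default; section 9.3.2.5 collects a start date and time to onset and says nothing more. The convention for unknown onset is commonly left to the SAP, which is not shown, so its absence here is not a fault.

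Nor do the documents say that imaging takes place on treatment but not before. Section 9.3.2.7 refers to imaging in clinical practice as the label recommends, and a pre-dose or first-intake assessment is in the schedule. That the protocol mandates no imaging applies equally to on-treatment images. Sites that do not image before dosing may also image less afterwards, which would shrink the effect.

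Finally, counting every fracture is a defensible conservative choice in a safety registry. Restricting the headline to proven new fractures would understate an identified risk, and would conflict with the TEAE condition that admits pre-existing events that worsened.

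All of this stands, and it rules out changing the TEAE definition or the main count. It does not answer the narrower point: the AESI and fracture tables, as specified, combine old and new fractures and do not use the imaging data that could tell them apart.

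**Conclusion.** The point holds in a limited form. Fracture and AESI incidence can be biased upward by vertebral fractures that pre-date the first dose, and serious-TEAE incidence may be, depending on how unknown onset is handled. The claim that the primary safety endpoint as a whole is inflated is not supported: all-TEAE incidence has about 2.2 points of room if the earlier skin-reaction rate carries over, and the analyses are descriptive (section 9.7.3.1).

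The size is unknown. The range of 0.4 to 20.1 participants out of 67 rests wholly on assumed prevalence and imaging shares, and falls to zero if every old fracture was imaged before dosing. The figures show that the mixing could matter, not that it does.

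The conflict between Table 3 and section 9.2.7.1 is real but separate. Non-naïve participants have already been dosed by Baseline, so restoring that assessment would not supply a pre-dose image. It would help to place a fracture before or after consent, which matters because section 9.3.2.7 records the two on different forms.

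**What to change.** In section 9.7.3.4, and for fracture AESIs in section 9.7.3.2:
- Keep the count of all reported fractures, and leave the TEAE definition unchanged, including the condition for events that worsened.
- Add a split of radiological vertebral fractures by the spinal imaging already collected: new since an earlier image, seen on a pre-dose image, or no earlier image (onset undetermined).
- Report incidence with and without the undetermined group.
- Tie pre-dose to one named date. Section 9.7.3.2 refers both to the first marketed dose and to the first dose of palovarotene, and these differ for anyone with earlier investigational use.

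Separately, reconcile Table 3 with section 9.2.7.1 on the Baseline spinal assessment for non-naïve participants.

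The cost is an additional table row and one status item on the fracture form, best added early because pre-dose status is hard to recover after years of follow-up. No imaging is added, and reporting to pharmacovigilance is unchanged. The drawback is that an undetermined group will be visible in the results and, if large, will leave the incidence of new fractures as a range.

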### **Events NOT Meeting the AE Definition**

Any clinically significant abnormal laboratory findings or other abnormal safety assessments which are associated with the underlying disease, unless judged by the investigator to be more severe than expected for the participant's condition.

The disease/disorder being studied or expected progression (e.g. flare-up), signs, or symptoms of the disease/disorder being studied, unless judged by the investigator to be more severe than expected for the participant's condition.

Medical or surgical procedure (e.g. endoscopy, appendectomy): the condition that leads to the procedure is the AE.

**PAGE 75 OF 287** 

Situations in which an untoward medical occurrence did not occur (social and/or convenience admission to a hospital).

Anticipated day-to-day fluctuations of pre-existing disease(s) or condition(s) present or detected at the start of the study that do not worsen.

### 11.1.2 Serious Adverse Event

If an event is not an AE per definition above, then it cannot be an SAE even if serious conditions are met (e.g. hospitalisation for signs/symptoms of the disease under study, death due to progression of disease).

An SAE is defined as any untoward medical occurrence that, at any dose:

### Results in death

# Is life-threatening

The term 'life-threatening' in the definition of 'serious' refers to an event in which the participant was at risk of death at the time of the event. It does not refer to an event, which hypothetically might have caused death, if it were more severe.

### Requires inpatient hospitalisation or prolongation of existing hospitalisation

In general, hospitalisation signifies that the participant has been detained (usually involving at least an overnight stay) at the hospital or emergency ward for observation and/or treatment that would not have been appropriate in the physician's office or outpatient setting. Complications that occur during hospitalisation are AEs. If a complication prolongs hospitalisation or fulfils any other serious criteria, the event is serious. When in doubt as to whether 'hospitalisation' occurred or was necessary, the AE should be considered serious.

Hospitalisation for elective treatment of a pre-existing condition that did not worsen from Baseline is not considered an AE.

### Results in persistent disability/incapacity

The term disability means a substantial disruption of a person's ability to conduct normal life functions.

This definition is not intended to include experiences of relatively minor medical significance such as uncomplicated headache, nausea, vomiting, diarrhoea, influenza and accidental trauma (e.g. sprained ankle) which may interfere with or prevent everyday life functions but do not constitute a substantial disruption.

### Is a congenital anomaly/birth defect

### Other important medical event

Medical or scientific judgment should be exercised in deciding whether SAE reporting is appropriate in other situations such as important medical events that may not be immediately life-threatening or result in death or hospitalisation but may jeopardise the participant or may require medical or surgical intervention to prevent one of the other outcomes listed in the above definition. These events should usually be considered serious.

Examples of such events include invasive or malignant cancers, intensive treatment in an emergency room or at home for allergic bronchospasm, blood dyscrasias or convulsions that do not result in hospitalisation, or development of drug dependency or drug abuse.

**PAGE 76 OF 287** 

Any radiological or clinical fracture, or PPC, must be reported as serious (seriousness criteria should be "important medical event" if no other seriousness criteria are present (e.g. hospitalisation)).

Is a suspected transmission of any infectious agent via an authorised medicinal product

### 11.1.3 Special Situations

A Special Situation is any incidence of drug exposure during pregnancy (i.e. drug exposure to a foetus in utero (whether the foetus is exposed via the mother taking the product)) or breastfeeding, overdose, underdose, off-label use, misuse, abuse, occupational exposure, medication errors/Intercepted medication error/Potential medication error, counterfeit/falsified medicinal product, unexpected therapeutic benefit, suspected transmission of an infectious agent via a medicinal product, drug interaction, drug dependence or lack of therapeutic effectiveness whilst using the medicinal product. A "Special Situation" should be collected by the investigator and reported to Ipsen whether or not these "Special Situations" are associated with an AE.

### 11.1.3.1 Pregnancy or Breastfeeding

### Pregnancy

Palovarotene is highly teratogenic and must not be used by participants who are or may become pregnant.

In accordance with the label, if pregnancy occurs in a participant exposed to palovarotene, treatment must be stopped immediately, and the participant should be referred to a physician for evaluation and advice. Participants of child-bearing potential must use at least one highly effective method of contraception (e.g. intrauterine device (IUD)) or two effective methods (e.g. combined hormonal contraception in combination with another method of contraception such as a barrier method) during the course of the study.

Pregnancy itself is not regarded as an AE unless there is a suspicion that the product has interfered with a contraceptive method. If pregnancy occurs while enrolled in FOPal, the outcome of the pregnancy will then need to be collected. This applies irrespective of whether the pregnancy is considered to be related to interference with a contraceptive method by the product.

The following maternal, neonatal, and infant outcomes will be assessed:

- Maternal outcomes:
  - Foetal loss: miscarriage, spontaneous abortion, stillbirth, elective or therapeutic abortion, foetal loss type not specified.
- Neonatal outcomes (from birth to one month):
  - Neonatal death with or without congenital abnormalities (major or minor);
  - Live birth with congenital abnormalities (major\* and minor);
  - Live birth without congenital abnormalities;
  - Preterm birth;
  - Small for gestational age.
  - \* Major birth defects are defined as major structural or genetic birth defects as conditions that 1) result from a malformation, deformation, or disruption in one or more parts of the body, a chromosomal abnormality, or a known clinical syndrome; 2) are present at birth; and 3) have a serious, adverse effect on health, development, or functional ability.

**PAGE 77 OF 287** 

- Infant outcomes (from one month to one year, end of follow-up period):
  - Infant death;
  - Postnatal growth deficiency;
  - Infant developmental delay;
  - Infant hospitalisation due to serious illness.

Details of all pregnancies in participants will be collected from the signing of the ICF and the participant will be followed through the first year postpartum to monitor pregnancy-related AEs, and the birth and developmental outcomes through the infant(s)' first year of life. The following monitoring schedule is recommended for data collection:

- Baseline;
- Mid-pregnancy;
- Estimated Due Date (EDD);
- EDD + 6 months;
- EDD + 12 months.

For live-born infants, data should be assessed at 3 timepoints during the data collection: at EDD; EDD + 6 months; and EDD + 12 months.

Information regarding any pregnancies must be collected on the electronic data collection tool or the "Adverse Event and Other Safety Events Report Form for Company-Sponsored Non-Interventional Studies" (134232-FOR) if the electronic data collection tool is unavailable. Pregnancy information, including birth and developmental status of the infant will also be collected in the Drug Exposure During Pregnancy Form for Company-Sponsored Clinical Studies (458088-FOR) and should be provided for all pregnancies, regardless of the outcome.

Abnormal pregnancy outcomes (such as spontaneous abortion, foetal death, stillbirth, livebirth with congenital abnormalities (major and minor), ectopic pregnancy, termination of pregnancy, preterm birth, small for gestational age or foetal growth restriction, neonatal or infant death, and any other foetal or infant abnormalities that may be medically important) are considered SAEs.

Reports of pregnancy must be reported to Ipsen within 24 hours of the investigator's knowledge.

